4.2.1.3 Planned Exploratory Biomarker Research

4.2.1.3.1 Planned Genetic Analysis

Genetic variation may impact a participant's response to therapy, susceptibility to, severity, and progression of disease. Variable response to therapy may be due to genetic determinants that impact drug absorption, distribution, metabolism, and excretion; mechanism of action of the drug; disease etiology; and/or molecular subtype of the disease being treated. Therefore, where local regulations and IRB/IEC allow, a sample will be collected for DNA analysis from consenting participants.

DNA samples will be used for research related to the study intervention(s), the disease under study, and related diseases. They may also be used to develop tests/assays including diagnostic tests related to the disease under study, related diseases, and study intervention(s). Genetic research may consist of the analysis of 1 or more candidate genes or the analysis of genetic markers throughout the genome [or analysis of the entire genome] (as appropriate).

DNA samples will be analyzed for variation across the entire genome. Analyses may be conducted if it is hypothesized that this may help further understand the clinical data.

The samples may be analyzed as part of a multi-study assessment of genetic factors involved in the response to understand study disease or related conditions.

4.2.1.4 Future Biomedical Research

The Sponsor will conduct future biomedical research on DNA specimens for which consent was provided during this clinical study.

Such research is for biomarker testing to address emergent questions not described elsewhere in the protocol (as part of the main study) and will only be conducted on specimens from appropriately consented participants. The objective of collecting/retaining specimens for future biomedical research is to explore and identify biomarkers that inform the scientific understanding of diseases and/or their therapeutic treatments. The overarching goal is to use such information to develop safer, more effective drugs/vaccines, and/or to ensure that participants receive the correct dose of the correct drug/vaccine at the correct time. The details of this future biomedical research substudy are presented in Appendix 6.

4.2.2 Rationale for the Use of Comparator/Placebo

No comparator or placebo arm is included in this study. This study will be conducted as double dummy study and as appearance of MK-7264 45 mg and 15 mg tablets are different, matching placebos are used to maintain blinding.

4.3 Justification for Dose

4.3.1 Doses for This Study

The dose for this study will be either MK-7264 45 mg BID or MK-7264 15 mg BID as determined by the individual allocation per the assigned treatment group (see Section 6).

The known mechanism of action of MK-7264 and related clinical study results support that the efficacy of MK-7264 in decreasing cough, and the prevalence of the most common AE, dysgeusia, are both dose related. In order to allow patients and prescribers appropriate flexibility based upon individual clinical needs, the MK-7264 development program has targeted two different doses to study in the Phase 3 program.

4.3.2 Maximum Dose/Exposure for This Study

The maximum dose/exposure for this study will be at 45 mg BID. Participants who are administered MK-7264 (either 15 mg BID or 45 mg BID) will be exposed to MK-7264 for approximately 52 weeks.

4.3.3 Rationale for Dose Interval and Study Design

In this study, MK-7264 will be orally administered as MK-7264 45 mg BID or 15 mg BID based on the safety and pharmacokinetic efficacy results observed to date (refer to the IB).

Based on pharmacokinetic studies, MK-7264 is rapidly absorbed with a median time to reach maximum plasma concentration (T_{max}) of 1.0 to 2.0 hours. In addition, the half-life of MK-7264 is approximately 7 to 10 hours and consistent with a BID dosing schedule.

The duration of treatment is up to 1 year in order to provide a more robust assessment of the long-term safety, tolerability and efficacy of MK-7264 in the treatment of refractory or unexplained chronic cough.

4.4 Beginning and End of Study Definition

The overall study begins when the first participant signs the ICF. The overall study ends when the last participant completes the last study-related telephone-call or visit, withdraws from the study, or is lost to follow-up (ie, the participant is unable to be contacted by the investigator).

4.4.1 Clinical Criteria for Early Study Termination

There are no prespecified criteria for terminating the study early.

5 STUDY POPULATION

Male/Female participants with chronic cough \geq 4 months and a diagnosis of refractory or unexplained chronic cough at least 20 years of age will be enrolled in this study. For the purposes of this study, refractory chronic cough is defined as participants who have had a clinical evaluation that suggested a co-morbid condition that may be related to cough (eg, gastroesophageal reflux disease [GERD], asthma, or upper airway cough syndrome), the participant has received appropriate diagnostic workup and therapy according to the Japanese Respiratory Society (JRS) guidelines, and the participant continues to cough despite being on therapy. Also in this study, unexplained chronic cough is defined as participants who have had a clinical evaluation of their cough per JRS guidelines and this evaluation has not suggested a co-morbid condition that may be related to cough.

Prospective approval of protocol deviations to recruitment and enrollment criteria, also known as protocol waivers or exemptions, is not permitted.

5.1 Inclusion Criteria

Participants are eligible to be included in the study only if all of the following criteria apply:

Type of Participant and Disease Characteristics

1. Chest radiograph or computed tomography scan of the thorax (within 5 years of Visit 1 and after the onset of chronic cough) not demonstrating any abnormality considered to be significantly contributing to the chronic cough or any other clinically significant lung disease in the opinion of the principal investigator or the sub-investigator.
2. Have cough for \geq 4 months at signing informed consent and a diagnosis of refractory or unexplained chronic cough as specified in Section 5.
3. The participant has persistent cough despite of treatment in accordance with the latest guideline of cough from the Japanese Respiratory Society and is burden to the participant and need further treatment in the opinion of the principal investigator or the sub-investigator.

Demographics

4. Participant is Japanese Male or Female from 20 years of age inclusive, at the time of signing the informed consent.

Female Participants

5. A female participant is eligible to participate if she is not pregnant (Appendix 5), not breastfeeding, and at least 1 of the following conditions applies:
 - a. Not a woman of childbearing potential (WOCBP) as defined in Appendix 5.

OR

- b. A WOCBP who agrees to follow the contraceptive guidance in Appendix 5 from signing informed consent to 14 days after the last dose of study intervention.

Informed Consent

6. The participant is able to provide written informed consent for the study on their own behalf. The participant may also provide consent for Future Biomedical Research. However the participant may participate in the main study without participating in Future Biomedical Research.

Study Participation

7. The participant is willing and able to comply with all aspects of the protocol including demonstrating an ability to follow study procedures (including completion of the patient report outcomes [PROs]) to the satisfaction of the investigator/qualified designee prior to randomization (see Section 8.1.2).

5.2 Exclusion Criteria

Participants are excluded from the study if any of the following criteria apply:

Medical Conditions

1. Current smoker.
2. Individuals who have given up smoking within 12 months of Visit 1.
3. Forced expiratory volume in 1 second (FEV₁)/ forced vital capacity (FVC) ratio <60% (spirometry performed within the past year and after the onset of chronic cough is acceptable if the investigator confirms that spirometry was done during a period where the participant was clinically stable (eg, not during an upper respiratory infection)).
4. History of upper or lower respiratory tract infection or recent clinically significant change in pulmonary status within 4 weeks of Visit 1.
5. History of chronic bronchitis, defined as a cough that produces a clinically significant amount of sputum (greater than approximately 1 tablespoon of phlegm) that occurs every day for at least 3 months in a row, with those periods occurring at least 2 years in a row.
6. Individuals who are currently taking an angiotensin converting enzyme inhibitor or have taken an angiotensin converting enzyme inhibitor within 3 months of signing informed consent.
7. Estimated glomerular filtration rate (eGFR) <30 mL/min/1.73 m² at Screening OR eGFR ≥30 mL/min/1.73 m² and <50 mL/min/1.73 m² at Visit 1 with unstable renal function (defined as a ≥50% increase of serum creatinine compared to a value obtained at least 6 months prior to Visit 1).
8. Has a history of malignancy ≤ 5 years prior to signing informed consent except for adequately treated basal cell or squamous cell skin cancer or in situ cervical cancer.
9. Is, at the time of signing informed consent, a user of recreational or illicit drugs or has had a recent history (within the last year) of drug or alcohol abuse or dependence in the opinion of the principal investigator or the sub-investigator.
10. Systolic blood pressure >160 mm Hg or a diastolic blood pressure >90 mm Hg at Visit 1.

11. History of anaphylaxis or cutaneous adverse drug reaction (with or without systemic symptoms) to sulfonamide antibiotics or other sulfonamide-containing drugs.
12. Has a known allergy/sensitivity or contraindication to MK-7264 or its excipients.(note: refer to the IB for details regarding excipients for MK-7264)
13. Has donated or lost ≥ 1 unit of blood (approximately 300 mL) within 8 weeks prior to the first dose of MK-7264.
14. A WOCBP who has a positive urine and serum pregnancy test at Visit 1. If the urine test is positive or cannot be confirmed as negative, a serum pregnancy test is required.

Prior/Concomitant Therapy

15. Requiring treatment with a therapy that does not adhere to the guidance parameters specified in Section 6.5.

Prior/Concurrent Clinical Study Experience

16. Has previously received MK-7264 (excluding participants who received MK-7264 and completed the treatment in Protocol 033).
17. Is currently participating in or has participated in an interventional clinical study with an investigational compound or device within 30 days of participating in this current study.

Diagnostic Assessments

18. Significantly abnormal laboratory tests at Visit 1 (see Section 8.3.6), including:
 - a. alkaline phosphatase (ALP), alanine aminotransferase (ALT, SGPT), aspartate aminotransferase (AST, SGOT) $>200\%$ of the upper limit of normal, or bilirubin $>150\%$ of the upper limit of normal.
 - b. hemoglobin <10 g/dL, white blood cell count (WBC) <2500 / μ l, neutrophil count <1500 / μ l, platelet count $<10 \times 10^4$ / μ l.

For any of the above listed laboratory assessments, 1 repeat measurement will be allowed at the investigator's discretion, before being considered a screen failure.

Other Exclusions

19. Has history or current evidence of any condition, therapy, laboratory abnormality or other circumstance that may increase the risk associated with study participation or investigational product administration or may interfere with the interpretation of study results and, in the judgment of the investigator or Sponsor, would make the participant inappropriate for entry into this study.

20. Is or has an immediate family member (eg, spouse, parent/legal guardian, sibling, or child) who is investigational site or Sponsor staff directly involved with this study. Is or has an immediate family member (eg, spouse, parent/legal guardian, sibling, or child) who is investigational site or Sponsor staff directly involved with this study.

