2.1 Study Rationale

The purpose of this study is to evaluate the long-term safety of MK-7264, an orally available P2X3 antagonist, in adult Japanese participants, at least 20 years of age, who have either refractory or unexplained chronic cough.

Current therapies for cough (narcotic, non-narcotic, and over-the-counter medications) have limited and/or unproven efficacy and an undesirable side effect profile. There are currently no approved therapies for chronic cough.

Previous Phase 2 studies have demonstrated dose-related efficacy and an acceptable safety and tolerability for MK-7264 in non-Japanese adult participants with refractory and unexplained chronic cough (refer to the Investigator's Brochure [IB]). The purpose of this study is to evaluate the long-term safety of MK-7264 with regulatory required number of Japanese refractory or unexplained chronic cough patients.

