3 HYPOTHESIS, OBJECTIVES, AND ENDPOINTS

There are no hypothesis for this study.

In this study, the objectives and endpoints below will be evaluated by treatment group and combined in Japanese adult participants with refractory or unexplained chronic cough.

Objectives	Endpoints
Primary	

To evaluate the safety and tolerability of MK-7264 through 52 weeks	
Adverse event (AE)Study treatment discontinuations due to AE
Secondary	

To evaluate the efficacy of MK-7264 in improving cough specific quality of life with change from baseline at Week 12 and through 52 weeks	
Leicester Cough Questionnaire (LCQ)
Exploratory	

To evaluate the efficacy of MK-7264 in improving self-rated cough severity with change from baseline at Week 12 and through 52 weeks	
Cough Severity Diary (CSD)

To evaluate the impact of MK-7264 on generic health-related quality of life and global rating of change through 52 weeks	
EuroQoL 5 Version Five Dimensions Questionnaire (EQ5D-5L)Patient Global Impression of Change (PGIC)

To explore the relationship between genetic variation and response to the treatment(s) administered, and mechanisms of disease. Variation across the human genome may be analyzed for association with clinical data collected in this study.	
Germline genetic variation

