3.5.2 Safety Analysis Populations

The APaT population will be used for the analysis of safety data in this study. The APaT population consists of all randomized participants who received at least one dose of study treatment. Participants will be included in the treatment group corresponding to the study treatment they actually received for the analysis of safety data using the APaT population. Discontinued participants before Week 52 will be included in APaT population. For most participants this will be the treatment group to which they are randomized. Participants who take incorrect study treatment for the entire treatment period will be included in the treatment group corresponding to the study treatment actually received.

If a participant is found to have taken one or more incorrect doses of study medication from that to which he/she was randomized, then the participant will be counted in the higher dose arm he/she actually received; that is, if a participant was originally randomized to MK-7264 15 mg but during the course of the study has taken 1 or more doses of MK-7264 45 mg, then the participant will be included in the MK-7264 45 mg treatment arm in the safety analysis.

At least one laboratory or vital sign measurement obtained subsequent to at least one dose of study treatment is required for inclusion in the analysis of each specific parameter. To assess change from baseline, a baseline measurement is also required.

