3.6 Statistical Methods

The results will be provided by treatment group and total (combined treatment group). There is no plan to do between treatment group comparisons.

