3.6.3 Summaries of Baseline Characteristics, Demographics, and Other Analyses

Demographic and Baseline Characteristics

The number and percentage of participants screened, randomized, the primary reasons for screening failure, and the primary reason for discontinuation will be displayed.

Demographic variables (including age, gender, weight, and height), baseline characteristics, primary and comorbid conditions, and prior and concomitant therapies will be summarized either by descriptive statistics or categorical tables.

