3.10 Subgroup Analyses and Effect of Baseline Factors

No subgroup analysis is planned in this study.

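### Does re-admitting Protocol 033 completers, with no separate analysis of them, distort the primary safety percentages?

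*Combined protocol and SAP*

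**What the plan says.** Protocol Section 5.2, exclusion 16, rules out a person who "Has previously received MK-7264 (excluding participants who received MK-7264 and completed the treatment in Protocol 033"). On that wording, someone who stopped early in Protocol 033 stays out, and so does anyone who received the drug in another study, whether or not they completed it.

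Protocol Section 3 lists "Study treatment discontinuations due to AE" as a primary endpoint beside adverse events. Section 2.1 gives the purpose as to "evaluate the long-term safety of MK-7264 with regulatory required number of Japanese refractory or unexplained chronic cough patients". Section 4.2.2 states: "No comparator or placebo arm is included in this study".

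For the analysis, sSAP Section 3.5.2 says: "The APaT population consists of all randomized participants who received at least one dose of study treatment". sSAP Section 3.6 says: "The results will be provided by treatment group and total (combined treatment group"), and it plans no comparison between the two doses. sSAP Section 3.10 adds: "No subgroup analysis is planned in this study". At baseline, sSAP Section 3.6.3 provides that "prior and concomitant therapies will be summarized either by descriptive statistics or categorical tables".

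**The concern.** Among prior recipients, entry depends on not having stopped the drug early. That is close in kind to a primary endpoint of this study, so the re-admitted group could be enriched for people who tolerate MK-7264. They are pooled with first-time users, randomization is not stratified (Protocol 6.3.2), and the number of Protocol 033 completers is not capped.

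Without a control arm, the absolute percentages are the primary result, and the Week 24 results go into the Japanese filing (Protocol 4.1). If many tolerant re-entrants enrolled, the reported percentage stopping for an adverse event could understate the rate in patients starting the drug, and no planned table would show it.

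**Working it through.** **1. What the percentages are meant to estimate.** Protocol Sections 2.1 and 3 set the question as 52-week safety in Japanese adults with refractory or unexplained chronic cough. No section restricts it to patients new to MK-7264. A population of all treated participants, reported by dose and combined, matches that question. A rate in first-time users is a different quantity, which the plan does not claim to estimate.

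**2. Which inputs the documents supply.** Planned enrolment is 160, randomized 1:1, so about 80 per dose (Protocol 4.1 and 9.9). Protocol 2.2.2 describes Protocol 033 only as a phase 2 study in Japanese patients that has been completed; it gives no size, dose, duration or number of completers. Three inputs are therefore assumptions: the share of re-admitted completers *f*, the first-time rate *p*, and the completers' risk relative to first-time users *RR*.

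**3. Check against the plan's own figures.** The exact two-sided 95% upper bound after zero events is 1 - 0.025^(1/n). It gives 4.30% at n = 84 and 8.41% at n = 42, matching the stated 4.3% and 8.4%. Neither figure depends on prior exposure.

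**4. Size of a possible shift.** Pooled rate = p × [1 - f × (1 - RR)], so shift = -p × f × (1 - RR). For example, p = 15%, f = 10%, RR = 0.5 gives -15 × 0.10 × 0.5 = -0.75 points. The half-width is 1.96 × √(p(1 - p)/160).

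| Assumed p | f = 10%, RR 0.5 / 1.25 | f = 25%, RR 0.5 / 1.25 | Half-width, n = 160 |
|---|---|---|---|
| 5% | -0.25 / +0.13 | -0.63 / +0.31 | 3.38 |
| 15% | -0.75 / +0.38 | -1.88 / +0.94 | 5.53 |
| 25% | -1.25 / +0.63 | -3.13 / +1.56 | 6.71 |

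All values are in percentage points. The shift is zero if *f* = 0 or *RR* = 1, and it changes sign if *RR* exceeds 1. The sign is open: a lower risk in completers is plausible, but Protocol 2.3 describes taste events as mechanism-based and reversible on stopping, so they could recur on re-exposure.

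**5. Where the shift would exceed sampling error.** Take p = 30%, f = 30%, RR = 0. The shortfall is 30 × 0.30 × 1 = 9.0 points, which puts the pooled rate at 21.0%, below the exact 95% interval for an observed 30% at n = 160 (23.0% to 37.7%). This needs 0.30 × 160 = 48 prior completers, none of whom stops for an adverse event in 52 weeks. Nothing in the documents points to such a case.

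**6. Whether a separate table would answer the question.** At f = 10% there would be 16 completers and 144 first-time users, so a table of first-time users would repeat most of the main one. Whether selection matters depends on the completers' own rate. At 15%, its half-width is 1.96 × √(0.15 × 0.85/16) = 17.5 points; with 40 completers (f = 25%) it is 11.1 points. If RR were 0.5, the difference to detect would be 15 - 7.5 = 7.5 points. Even at a completer rate of 7.5%, the half-widths are 12.9 points (n = 16) and 8.2 points (n = 40). Per dose the counts halve. The normal approximation is crude at these sizes, but the conclusion is not close.

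**The case for a change.** The strongest reply is that a composition effect is systematic: the confidence interval does not cover it, so a shift smaller than the half-width is not thereby harmless. Readers will also tend to apply the percentage to patients starting treatment. A descriptive split would be cheap, would leave the main analysis untouched, and would cost little precision: the zero-event bound rises only from 2.28% (n = 160) to 2.53% (n = 144) or 3.03% (n = 120).

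The first point stands as a principle, which is why the comparison with sampling error only gives scale and does not decide the matter. What decides it is that the pooled percentage answers the stated question. The second point calls for care in describing the population when results are reported; it does not make the planned estimate wrong. The third shows that the addition would be affordable, not that it is needed.

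The plan also leaves room to look. Medication history is taken at Visits 1 and 2 (Protocol 1.3), prior medication is recorded under Protocol 8.1.5.1, and prior therapies are tabulated. Protocol Section 9 allows exploratory analyses after the fact if they are labelled as such. The explicit one-year look-back for cough treatments (Protocol 6.5) could miss older Protocol 033 exposure, and whether the case report form captures it separately cannot be seen from the documents. With no hypothesis and no planned comparison between doses, specifying this split in advance would add little.

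**Conclusion.** The concern does not hold. The description of the plan behind it is accurate: only Protocol 033 completers are re-admitted, everyone treated is pooled, and no subgroup analysis is planned. But the study asks about Japanese patients with refractory or unexplained chronic cough, and the planned analysis answers that question as written.

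The documents cannot establish any distortion relative to first-time users, because *f*, *RR* and *p* are all missing. On the moderate assumptions in the table the shift is -3.1 to +1.6 points, smaller than the sampling half-width in every row; it exceeds sampling error only under assumptions such as those in step 5. The conclusion rests on the target population as stated in Protocol Sections 2.1 and 3. It would need another look if the results were presented specifically as rates in patients new to the drug.
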